5.4 Randomisation Procedures

Eligible patients who have given written, informed consent and who meet all the inclusion criteria and no exclusion criteria will undergo 1:1:1 randomisation to an un-blinded treatment of either AVATAR-protocol AF Ablation, medical anti-arrhythmic therapy or conventional AF ablation. Randomisation will be performed electronically using the InForm electronic data capture system and will be stratified by site.

From the date of randomisation, the 1st Intervention date (ablation or anti-arrhythmic medication change) must occur 28 days ± 7days after this, therefore an ablation procedure date will be identified according to local EP catheter lab availability for each consenting, eligible patient and randomisation of the patient will then be scheduled for 28 days ± 7days from this available date.

The patient may be withdrawn from any AF ablation treatment by the Investigator if any safety concerns arise during the period between randomisation and the ablation which make the patient an unsuitable candidate for the procedure. The patient will then be withdrawn from the study.

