5.3 Exclusion Criteria

Subjects with any of the following will be excluded from the study:

1. Contraindication to catheter ablation
2. No carer to enable daycare discharge
3. Documented Arrhythmias other than AF unless they have had curative ablation (eg. for atrial flutter)[§]
4. No documentation of sinus rhythm within 3 months
5. Valvular or coronary heart disease needing regular follow up
6. EF <45% or moderate/severe LV dysfunction(determined by Echocardiogram in the last 6 months)

7. Active gastrointestinal disease precluding anticoagulation or trans-oesophageal echocardiogram
8. Renal failure with creatinine $>200 \text{ }\mu\text{mol/L}$ or on dialysis
9. Active fever or infection
10. Life expectancy shorter than the trial
11. Allergy to contrast
12. Severe cerebrovascular disease
13. Bleeding or clotting disorders or inability to receive heparin
14. Uncontrolled diabetes (HbA1c $\geq 73 \text{ mmol/mol}$ or HbA1c $\leq 64 \text{ mmol/mol}$ and Fasting Blood Glucose $\geq 9.2 \text{ mmol/L}$) (shown in the last six months without evidence of being brought under control)*
15. Serum Potassium $[\text{K}^+] < 3.5 \text{ mmol/L}$ or $> 5.0 \text{ mmol/L}$ (shown in the last six months without evidence of being brought under control)
16. Malignancy needing surgery, chemotherapy or radiotherapy
17. Pregnancy or women of child-bearing potential not using a highly effective method of contraception **
18. Must not have previous (4 weeks prior to screening) or current participation in another clinical trial with an investigational drug or investigational device
19. Unable to give informed consent
20. Uncontrolled thyroid disease defined as abnormal thyroid function tests causing cardiac manifestations within the last 6mths21. Unable to attend follow up visits

§ AVATAR-AF Guidance on Atrial Flutter

- (I) **12 lead ECG documentation of typical atrial flutter during screening**
 - *Patient should not be recruited to the AVATAR study and should undergo Cavo-Tricuspid Isthmus line(CTI) ablation.*
 - *If symptomatic atrial fibrillation is still present then the patient can be considered for AVATAR recruitment.*
- (II) **12 lead ECG documentation of typical atrial flutter after randomisation.**
 - *Patient should be suspended from the AVATAR study intervention and should undergo CTI ablation.*
 - *If symptomatic atrial fibrillation still present then the patient can be considered for AVATAR intervention.*

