11.2 Data Analysis

Primary outcome: Failure is counted when a patient experiences any hospital episode related to treatment for atrial arrhythmia. Patients are censored from their treatment group when they switch to a treatment other than that to which they were originally assigned or when they leave their treatment group without having experienced a hospital episode.

Data will be analyzed using the intention-to-treat principle and a p value of 0.05 or less will be considered significant. Primary outcome will be analysed using Kaplan-Meier statistics and differences will be tested using log-rank test and proportional hazards models. Other outcomes will be compared using t-test for continuous and Chi-square test or Fisher exact test for categorical variables and the appropriate generalized linear model will be used.

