5.7. Randomisation

Eligible patients who have given written, informed consent and who meet all the inclusion criteria and no exclusion criteria will undergo 1:1:1 randomisation to an un-blinded treatment of either AVATAR-protocol AF Ablation, medical anti-arrhythmic therapy or conventional AF ablation. Randomisation will be performed electronically using the InForm electronic data capture system and will be stratified by site.

From the date of randomisation, the 1st Intervention date (ablation or anti-arrhythmic medication change) must occur 28 days \pm 7days after this, therefore an ablation procedure date will be identified according to local EP catheter lab availability for each consenting, eligible

patient and randomisation of the patient will then be scheduled for 28 days \pm 7 days from this available date.

The patient may be withdrawn from any AF ablation treatment by the Investigator if any safety concerns arise during the period between randomisation and the ablation which make the patient an unsuitable candidate for the procedure. The patient will then be withdrawn from the study.

6. Analysis Set

All treatment evaluation will be performed on the principle of intention to treat (ITT) with additional per-protocol analyses ran alongside if defined (see Section 8). The per-protocol analysis set will consist of patients who received treatment originally allocated.

A sensitivity analysis will also be performed excluding patients who are withdrawn from the study between randomisation and start of treatment / 1st intervention. Any subjects that have withdrawn during this period will still be required to attend the end-of-study follow-up visit.

7. Variables of Analysis

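### Patients judged unsuitable for ablation after randomisation are withdrawn from the study, against the plan's own follow-up and ITT rules, and a never-treated patient has no defined time zero

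*Protocol*

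**What the plan says.** **Withdrawal.** Between randomisation and first intervention there is a gap of 28 days ± 7 days. Protocol 5.4 and SAP 5.7 say that in this gap a patient may be "withdrawn from any AF ablation treatment by the Investigator if any safety concerns arise during the period between randomisation and the ablation". Both continue: "The patient will then be withdrawn from the study".

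**Retention.** SAP 6 makes ITT the main principle and adds a sensitivity analysis "excluding patients who are withdrawn from the study between randomisation and start of treatment". It then says: "Any subjects that have withdrawn during this period will still be required to attend the end-of-study follow-up visit". Protocol 7.2 plans three-monthly telephone calls for all randomised patients, and Protocol 12 plans a complete dataset for them. Protocol 13.2 keeps patients given another treatment in follow-up and analysis. Protocol 14.3.2 says the ITT analysis covers all patients and defines discontinuation as full withdrawal of consent.

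**Another route to no treatment.** The flutter guidance in Protocol 5.3 (item II, flutter documented after randomisation) says: "Patient should be suspended from the AVATAR study intervention and should undergo CTI ablation". It adds: "If symptomatic atrial fibrillation still present then the patient can be considered for AVATAR intervention". This is not worded for one arm.

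**Clock.** Protocol 8.2 and SAP 7.1, 7.2 and 8.2 time endpoints from the first intervention. Protocol 7.3 and SAP 5.6 count the one-year visit from it.

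**Censoring.** Protocol 11.2 says: "Patients are censored from their treatment group when they switch to a treatment other than that to which they were originally assigned". The same rule covers anyone who drops out of an arm with no event so far. SAP 8.2 has no such rule.

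**The concern.** A site that follows Protocol 5.4 to the letter stops following a randomised patient whom SAP 6 wants in the main analysis. The decision is made after randomisation in an un-blinded trial and applies to ablation only. In the primary comparison, AVATAR versus drugs, this sentence can thin one arm on clinical grounds and has no stated equivalent in the other. In AVATAR versus conventional ablation it applies to both arms.

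If the patient is followed after all, the analysis still lacks a starting point. A patient with no first intervention has no time zero and no date from which to count the visit that SAP 6 requires. Taken literally, such a patient adds no time at risk. The ITT analysis and the SAP 6 sensitivity analysis could then rest on the same patients, and their agreement would show nothing.

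**Working it through.** The point rests on comparing the text. The arithmetic only gives a sense of scale.

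**1. Sections side by side, for a patient found unsuitable for ablation before the procedure**

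| Question | Protocol 5.4, SAP 5.7 | Other sections |
|---|---|---|
| In the study? | No | Yes: Protocol 13.2 if given another treatment; under 14.3.2 discontinuation means withdrawn consent |
| Followed up? | No | Yes: Protocol 7.2 and 12; end-of-study visit in SAP 6 |
| In the ITT set? | Not if withdrawn | Yes: Protocol 14.3.2; implied by SAP 6 |
| Time zero? | None | None stated in either document |

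An ablation date is identified before randomisation (Protocol 5.4), and the visit schedule in Protocol 9 lists allocation of a first-intervention date at screening. So a usable date exists, but no section applies it to someone who is never treated.

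**2. Bias if patients are left out of one arm**

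Assumptions: no true difference, 50% with an event, a fraction w of the AVATAR arm left out, and event rate p among those left out. The documents give neither w nor p.

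Remaining rate r = (0.5 − w·p)/(1 − w); apparent HR = ln(1 − r)/ln(0.5).

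Example, w = 0.05 and p = 0.80: r = (0.5 − 0.04)/0.95 = 0.484, HR = 0.955.

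| w (of 107) | p = 0.37 | p = 0.63 | p = 0.80 |
|---|---|---|---|
| 2% (about 2) | 1.008 | 0.992 | 0.982 |
| 5% (about 5) | 1.020 | 0.980 | 0.955 |
| 10% (about 11) | 1.042 | 0.959 | 0.907 |

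The sign depends on whether those left out would have done worse or better than average. With equal loss from both ablation arms and no true difference, the HR stays at 1.00.

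**3. Cost of keeping them**

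Inputs from Protocol 11.1: event proportions 0.63 (drugs), 0.40 (AVATAR) and 0.20 (conventional), 100 evaluable per arm, two-sided alpha 0.025 (z = 2.2414).

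HR = ln(1 − p_low)/ln(1 − p_high); d = 100·(p_low + p_high); Freedman power = Φ(√d·(1 − HR)/(1 + HR) − 2.2414).

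- Plan, versus drugs: HR = ln 0.60/ln 0.37 = 0.514 and d = 103, which matches the stated 103 events. Power = Φ(3.260 − 2.241) = 0.846; the documents state 0.80. That mismatch does not affect this point.
- Plan, versus conventional: HR = ln 0.80/ln 0.60 = 0.437, d = 60, power = Φ(3.036 − 2.241) = 0.787.

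Now let 5% of each ablation arm be untreated, with an assumed event rate of 0.63:

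- AVATAR: 0.95·0.40 + 0.05·0.63 = 0.4115. Conventional: 0.95·0.20 + 0.05·0.63 = 0.2215.
- Versus drugs: HR 0.533, d = 104.2, power 0.807.
- Versus conventional: HR 0.472, d = 63.3, power 0.729.

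At 2% the powers are 0.831 and 0.764; at 10% they are 0.762 and 0.668.

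**The case against.** The best defence is that the intention is clear. A sensitivity analysis that excludes these patients presupposes a main analysis that includes them. SAP 6 requires their final visit, and Protocol 14.3.2 asks for follow-up assessments as far as possible after early discontinuation. On this view, one loose sentence and a missing clock rule remain. That is a fair account of intent. It does not remove the contrary instruction that sites will read, nor does it supply a start date.

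Three stronger readings are tempting, and the documents do not support them.

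- *That patients leave the primary comparison only from the AVATAR arm.* Only the Protocol 5.4 sentence is specific to ablation. The censoring in Protocol 11.2 applies to every arm, including drug patients who cross to ablation as Protocol 8.3 allows. The flutter guidance and the withdrawal for a new tachycardia in Protocol 8.3 are not arm-specific either.
- *That the start date must be chosen with the data in view.* A date is allocated before randomisation, and the rule can still be fixed before the data are seen.
- *That serious events before ablation go unrecorded.* Protocol 10 and 10.5 collect adverse events from randomisation, and Protocol 10.1 requires serious arrhythmia-related events to be reported as such. A stroke in the gap would be captured.

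The defence is also right that the illustrated bias is small beside the planned HR of 0.514 when few patients are involved.

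**Conclusion.** The concern holds as an internal contradiction plus an undefined time zero, and should be fixed. The withdrawal sentence in Protocol 5.4 and SAP 5.7 cannot stand beside Protocol 7.2, 12, 13.2 and 14.3.2 and SAP 6. No section gives a start date for a never-treated patient in any arm. The Protocol 11.2 censoring rule adds to this: it conflicts with ITT and with Protocol 13.2, and it does not appear in SAP 8.2.

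No bias has been shown. Its size and direction are unknown because withdrawal and event rates are not given. Under the assumptions above, a one-arm loss of 2% to 5% moves the apparent HR to between about 0.96 and 1.02. The contradiction itself depends on none of those assumptions.

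**What to change.** 1. In Protocol 5.4 and SAP 5.7, say that the patient is withdrawn from the ablation treatment only, and stays in telephone and month-12 follow-up and in the ITT set unless consent is withdrawn. The investigator's decision not to ablate is untouched.
2. In Protocol 11.2, state that the ITT analysis does not censor these patients for not being ablated or for changing treatment.
3. Before the data are seen, name one time origin that exists for every randomised patient and use it for all of them in the ITT analysis. The first-intervention date allocated before randomisation is one candidate. Count the month-12 visit of never-treated patients from it. Do not use allocated dates for untreated patients and actual dates for treated ones, because time zero would then depend on what happens after randomisation. Time from actual first intervention and time from randomisation can be sensitivity analyses. Align Protocol 7.3 and 8.2 and SAP 5.6, 7.1, 7.2, 8.2 and 8.3.
4. Keep the SAP 6 exclusion as a sensitivity analysis.

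The cost is mainly wording, since the follow-up is already planned. A randomisation-clock analysis would also need non-serious arrhythmia-related hospital visits recorded during the gap of about 28 days. The statistical price is the dilution calculated above. It also makes a deficit against conventional ablation harder to detect, so the SAP 6 sensitivity analysis should be read beside the ITT result.

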6 TREATMENT ARMS

In the 4 week period (28 days ± 7days) between Randomisation and 1st Intervention, there will be no change to the patient's arrhythmia treatment: the treatment which the patient has been randomised to will only occur on the date of 1st Intervention. All three treatment arms will follow the same scheduling protocol regardless of intervention.

6.1 AVATAR-AF Ablation Protocol

Anticoagulation regime will be at physician's discretion according to established HRS/ESC guidelines guided by CHADS-VASC scoring system. Patients on anticoagulation may follow a continuous, bridging or without anticoagulation as per local protocol.

The procedure is performed under sedation or general anaesthetic according to local preference. TOE is performed according to local protocols. Femoral sheaths placed in the right femoral vein (ultrasound guidance allowed). A single transeptal puncture is performed under TOE, ICE, CS catheter or aortic pigtail guidance. If coronary sinus catheter is used, this should be performed without electrograms if possible.

Pulmonary venography taken. The sheath is exchanged for a Cryosheath or other suitable large sheath and an Arctic Front Advance balloon is used to occlude the PV to Grade 3/4 and deliver

2 x 3min cryoablations to each vein. Phrenic nerve monitoring will be done with a temporary transvenous pacing wire and box. No specialist EP catheters are deployed and no formal assessment of PVI is done. ACT kept above 300s. Reversal of heparin with Protamine is allowed.

Transthoracic Echo (hand-held echo with documentation sufficient), Hb check and groin survey at 6 hours post-procedure. If all are stable, the patient is discharged as a daycare procedure and given appropriate instructions and advice on potential concerns and process for seeking advice

Patient is given a date for possible 'redo' procedure at 10wks ± 7 days post ablation.

All medication is continued for 4 weeks post-ablation and then all agents being used for anti-arrhythmic effect are stopped.

6.1.1 Review 1 (8 weeks ± 7 days post-ablation)

The patient is first reviewed 8 weeks ± 7 days post ablation. If asymptomatic for palpitations, weekly improvement or not possible to assess in time scale then the patient is entered into discharge protocol at 12 weeks ± 14days.

If there are ongoing symptoms then the redo procedure (as scheduled post 1st Intervention ablation) will be performed which will be a conventional PVI using radiofrequency thermocool catheter and PV mapping catheter or according to local practice. A daycare approach is taken again as per first procedure and the patient is reviewed at 12 weeks ± 7days and if stable enters Discharge protocol at 12 weeks ± 14days.

6.2 Anti-arrhythmic therapy

The anti-arrhythmic agent or the change in dose that was discussed with the patient selected as the next line of treatment at the initial screening visit is initiated at the 1st Intervention date. The anti-arrhythmic treatment is chosen should be done in accordance with local practice and guidelines.

The patient will undergo 2 reviews prior to entering the Discharge protocol.

- ***Review 1 (4 weeks post-1st Intervention)***
- ***Review 2 (8 weeks post-1st Intervention)***

At each review, the patient can be left unchanged, have an increase in drug dose or change of agent as required. Review 1 at 4 weeks post 1st intervention can take place as a telephone follow up followed by a clinic visit if required. Following the 2 reviews, the patient enters the Discharge protocol at 12 weeks ± 14days.

6.3 Conventional AF Ablation

Patients randomised to the conventional AF Ablation arm will undergo the conventional Cryoablation procedure. This arm will be used as a second control arm to compare the differences in impact on healthcare resources, complication rates and clinical outcomes between conventional ablation and AVATAR-protocol ablation.

Anticoagulation regime will be physician discretion according to established HRS/ESC guidelines guided by CHADS-VASC scoring system. Patients on anticoagulation may follow a continuous, bridging or without anticoagulation as per local protocol.

The procedure is performed under sedation or general anaesthetic according to local preference. TOE is performed according to local protocols. Femoral sheaths placed in the right

femoral vein (ultrasound guidance allowed). A single or double transeptal puncture may be done guided by TOE, aortic pigtail, ICE or CS catheter guidance. Pulmonary venography taken. The sheath is exchanged for a Cryosheath or other suitable large sheath and an Arctic Front Advance balloon is used to occlude the PV to Grade 3/4 and deliver 2 x 3min cryoablations to each vein. Phrenic nerve monitoring can be according to local protocol.

The PV will be mapped using a circular mapping catheter of the operators choice and the number of veins isolated with this approach documented. PV isolation is completed with either repeat cryoballoon, deflectable cryotherapy catheter or radiofrequency catheter. The catheters used and outcomes documented.

The patient is monitored overnight and should have an Hb, groin and echo (handheld with documentation sufficient) check prior to discharge.

All medication is continued for 4 weeks post-ablation and then all agents being used for anti-arrhythmic effect are stopped.

6.3.1 Review 1 (8 weeks ± 7 days post-ablation)

The patient undergoing conventional AF ablation is also first reviewed 8 weeks ± 7 days post ablation. If asymptomatic for palpitations, weekly improvement or not possible to assess in time scale then the patient is entered into discharge protocol at 12 weeks ± 14days.

If there are ongoing symptoms then the redo procedure (as scheduled post 1st Intervention ablation) will be performed at 10wks

6.4 Redo Ablation (10 weeks± 7 days)

Anticoagulation regime will be physician discretion according to established HRS/ESC guidelines guided by CHADSVASC scoring system. Patients on anticoagulation may follow a continuous, bridging or without anticoagulation as per local protocol.

The procedure is performed under sedation or general anaesthetic according to local preference. TOE is performed according to local protocols. Femoral sheaths placed in the right femoral vein (ultrasound guidance allowed). A single or double transeptal puncture is performed under TOE, ICE, aortic pigtail or CS catheter guidance.

Pulmonary venography taken and PV mapping performed. Further ablation can be performed according to operator preference by radiofrequency ablation, Cryoballoon or cryocatheter.

Transthoracic Echo (hand-held echo with documentation sufficient), Hb check and groin survey at 6 hours post-procedure.

Patients in AVATAR-AF protocol arm are discharged as a daycare procedure and given appropriate instructions and advice on potential concerns and process for seeking advice.

Patients in conventional ablation arm are kept overnight.

All medication being used for anti-arrhythmic effect are stopped.

6.5 Discharge Review (Week 12± 14 days)

Patient will be assessed at week 12 for evidence of Primary and secondary endpoints. Patients will also be reviewed for suitability for entering discharge protocol.

7 ASSESSMENT AND FOLLOW-UP

7.1 Discharge Protocol

Patients from the all therapy arms will enter the Discharge protocol 12 weeks \pm 14days post-1st Intervention providing no ongoing symptoms are presented before this.

Patients will be given the centre's Research Nurse contact details and are able to request an unscheduled visit if they experience recurrent symptoms and need hospital review. A blinded research Nurse or designee will contact the patient by telephone every 3 months to ensure that no endpoints have occurred.

The patient will be advised that the blinded research Nurse or designee making the phone call will not know which treatment they have received and the patient will be given a copy of the questions that they will be asked.

7.1.1 Patients unable to enter the Discharge Protocol

Patients not able to enter the discharge protocol at 12 weeks will have necessary advice (further OPD, procedure) which will be a primary endpoint. The date of the endpoint will be the date of the subsequent event. These patients will be followed up at their usual study visits at M6, M9 and Final visit.

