8.3 Crossover between therapies

Following the week 12 visit, a patient from any group, the Investigator may initiate further drug therapy or schedule a standard ablation procedure for the patient. However, the following are required;

- i) *Ablation Arms (Conventional and AVATAR-AF):* Can start anti-arrhythmic drugs or further redo-ablation if there is ECG/Holter documentation of recurrent AF/AT
- ii) *Drug Therapy Arm:* May receive ablation therapy if failed one anti-arrhythmic at maximum standard dose or two anti-arrhythmic agents at sub-maximal dose or due to side effects.
- iii) *New tachycardia documented that needs treatment (VT/AVNRT/AVRT).* The patient is withdrawn from the study

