13.2 Consent

Consent to enter the study must be sought from each participant only after a full explanation has been given, an information sheet offered and time allowed for consideration. Signed participant consent must be obtained. The right of the participant to refuse to participate without giving reasons must be respected. After the participant has entered the study the clinician remains free to give alternative treatment to that specified in the protocol at any stage if he/she feels it is in the participant's best interest, but the reasons for doing so must be recorded. In these cases, the participants remain in the study for the purposes of follow-up and data analysis. All participants are free to withdraw at any time from the protocol treatment without giving reasons and without prejudicing further treatment.

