7.1. Primary Endpoint Variable

Time from 1st intervention to any hospital episodes (Emergency Room or patient request for OPD) related to treatment for atrial arrhythmia that has been formally adjudicated by an independent committee as a primary endpoint. Failure to enter discharge protocol at the Week 12 Review will also result in the primary endpoint being met.

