8.2. Primary Endpoint Analysis

Failure is counted when a patient experiences any hospital episode related to treatment for atrial arrhythmia. Time to failure will be taken as the time from 1st Intervention to the time of event.

Data will be analysed using the intention-to-treat principle and a p-value of 0.025 or less will be considered significant. Primary outcome will be analysed using Kaplan-Meier statistics and differences between treatment arms will be assessed using log-rank testing and proportional hazards models. Models containing one or more of the following covariates may also be assessed if deemed necessary; site, weight, hypertension, number of anti-arrhythmic taken by patient prior to 1st intervention.

Primary endpoint analysis will be carried out between AVATAR-AF Ablation and the Anti-Arrhythmic drug treatment arm in order to investigate the primary objective. The secondary objective will be assessed by testing AVATAR-AF Ablation against the Conventional Ablation arm.

An additional per-protocol analysis will be carried out in conjunction with the above.

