8.7. Tables to Present

Table 1.1: Subject Disposition

	Site A	Site B	...	Total
Screened				
Randomised				
Treatment A				
Treatment B				
Treatment C				
Withdrawn				
Reason for Withdrawal				
Completed				

Table 2.1: Listing of protocol deviations

Treatment	Subject	Site	Type	Start Date	End Date

Table 2.2: Number of protocol deviations by centre and category

Type of Deviation	Site A	Site B	...	Total
Patient was incorrectly included in the trial (did not meet all the inclusion and exclusion criteria)				
:				
Patient pregnancy				
Other				
Total				

Table 3.1: Baseline characteristics

Variable	Statistics	AVATAR-AF Ablation	Anti-arrhythmic therapy	Conventional AF Ablation
Age (y)	N Mean SD Min Median Max			
Race (n (%))	xxxxxx xxxxxx			
Ethnicity (n (%))	xxxxxx xxxxxx			
Gender (n (%))	Female Male			
Height (cm)	N Mean SD Min Median Max			
Weight (kg)	N Mean SD Min Median Max			
Pulse (bpm)	N Mean SD Min Median Max			
Systolic BP	N Mean			

	SD	
	Min	
	Median	
	Max	
Diastolic BP	N	
	Mean	
	SD	
	Min	
	Median	
	Max	
QoL Score	N	
	Mean	
	SD	
	Min	
	Median	
	Max	
QoL Score (n (%))	<40	
	...	
	90-99	
	100+	
Chadsvasc Score (n (%))	0	
	1	
	..	
	6	
AFEQT Score	N	
	Mean	
	SD	
	Min	
	Median	
	Max	
AFEQT Score (n (%))	0-19	
	...	
	80-100	

Anti-Arrhythmics Taken (n (%))	Amiodarone	
	...	
	Propafenone	
Beta Blockers Taken (n (%))	xxxxx	
Calc. Ch. Blocker Taken (n (%))	xxxxx	
Record of Anti-Coag Pre-Procedure (n (%))	Yes – Bridging	
	Yes – Continuous	
	No	
Expectation of Anti-Coag Post-Procedure (n (%))	Yes	
	No	
Subjects displaying evidence of Paroxysmal Atrial Fibrillation (n (%))	Yes	
	No	
ECG Rhythm (n (%))	Sinus	
	SVT	
	...	
	Q-Waves	
Ejection Fraction (%)	N	
	Mean	
	SD	
	Min	
	Median	
	Max	
Pericardial Effusion (n (%))	Yes	
	No	
Presence of Thrombus (n (%))	Yes	
	No	

***Table Note: To include the following variables - Age, race, ethnicity, gender, height, weight, pulse rate, Systolic BP, Diastolic BP, QoL Score, AFEQT Score, CHADSVASC Score, Heart Medications Taken, Record of Anti-Coagulation pre-procedure, Anti-Coagulation requirements post-procedure 24hr Holter, ECG, Echocardiology.**

PRIMARY ENDPOINT

Table 4.1: Listing of all hospital episodes (Emergency Room or patient request for OPD) related to treatment for atrial arrhythmia.

Treatment	Subj.	Date of Visit	Discharge Protocol?	Reason for Adjudication	Outcome	Endpoint?	Time to Event

Table 4.2: Log-rank test investigating occurrence of AF related hospital visits*

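### A week-12 discharge failure is a primary event in both documents, but Protocol and SAP conflict on how it is dated and on whether a treatment switch can censor it

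*Protocol*

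**What the plan says.** **Status.** Protocol 7.1.1 makes the onward advice given to a patient who cannot be discharged at week 12 (another outpatient visit, or a procedure) a primary endpoint. SAP 7.1 agrees that it counts: "Failure to enter discharge protocol at the Week 12 Review will also result in the primary endpoint being met".

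**Date.** Protocol 7.1.1: "The date of the endpoint will be the date of the subsequent event". SAP 7.1 gives no date for this kind of event. SAP 8.2 says only: "Time to failure will be taken as the time from 1st Intervention to the time of event". The shell for SAP Table 4.1 ("Listing of all hospital episodes (Emergency Room or patient request for OPD) related to treatment for atrial arrhythmia") has columns for visit date, discharge-protocol status and time to event, but states no rule.

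**Switching.** Protocol 8.3 says that after the week 12 visit, in any group and subject to conditions, "the Investigator may initiate further drug therapy or schedule a standard ablation procedure for the patient". Protocol 11.2: "Patients are censored from their treatment group when they switch to a treatment other than that to which they were originally assigned". That sentence goes on to censor patients who leave their group having had no hospital episode. The next paragraph of 11.2 adopts intention-to-treat, as does SAP 8.2, which has no switch-censoring rule. Protocol 13.2, on patients given alternative treatment, says: "In these cases, the participants remain in the study for the purposes of follow-up and data analysis".

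**The concern.** The primary log-rank and Cox analyses need one date and one event indicator per patient. For a week-12 failure, the documents leave three things open.

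1. **Which date.** The Protocol date is a later event that could be the first outpatient visit or the procedure. The SAP wording makes the failure at the Week 12 Review the event, which points to the review date without saying so.
2. **What if there is no later event in follow-up.** SAP 7.1 still counts the patient, but 7.1.1 supplies no usable date and neither document gives a fallback.
3. **Event or censored.** If the patient switches treatment before the subsequent event, Protocol 11.2 read literally censors first.

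Treatment is unblinded, and the conditions for the next step after week 12 differ by arm (Protocol 8.3). Waits and switches could therefore differ by arm too. Left open, the choice would be made after the data exist, in the primary analysis.

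**Working it through.** **The rules applied to four patients who fail discharge at week 12**

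| After week 12 | Protocol 7.1.1 with 11.2 | SAP 7.1 with 8.2 |
|---|---|---|
| Outpatient visit, no switch | Event at the visit | Event, date not stated |
| No later event by month 12 | Endpoint, but no date within follow-up | Event, date not stated |
| The procedure is itself the switch | Event and censoring on one date | Event, date not stated |
| Drug started in an ablation arm before the next visit | Switch precedes the 7.1.1 date: censored | Event, date not stated |

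In the third row the usual convention puts events before censorings, though no text says so. In the fourth row that convention does not help. The event count itself differs between the documents.

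**How far apart the dates can be.** Week 12 is day 84 and end of study is day 365, so nominally 365 − 84 = 281 days.

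**The plan's own figures** (Protocol 11.1, SAP 5.5). Inputs: 100 evaluable per arm, 0.63 v 0.40, two-sided 0.025.
- Events: 100 × 0.63 + 100 × 0.40 = 103, as stated.
- HR = ln(0.60)/ln(0.37) = 0.514.
- Freedman power = Φ(√103 × (1 − 0.514)/(1 + 0.514) − 2.241) = Φ(3.260 − 2.241) = 0.846. The plan states 0.80, so it is conservative here. That difference is a separate matter. The baseline for what follows is the simulated 0.82 to 0.84.

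**Illustration by simulation.** The documents give none of these inputs, so they are assumptions:
- A stated share of each arm's events are week-12 failures; other events are uniform over 12 months.
- The week-12 review is uniform over 2.30 to 3.22 months (days 70 to 98).
- The subsequent event follows after an exponential wait. Failures whose wait runs past month 12 are counted at month 12, since SAP 7.1 counts them. The share running late is exp(−(12 − 2.76)/mean wait): 1%, 10% and 21% for means of 2, 4 and 6 months.

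Power, log-rank at 0.025; waits are AVATAR v drug arm, mean months:

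| Dating, all failures counted | 50% share | 30% share | 10% share |
|---|---|---|---|
| At week 12, or equal 2-month waits | 0.82–0.84 | – | – |
| 1 v 2 | 0.77 | – | – |
| 1 v 4 | 0.69 | 0.77 | 0.81 |
| 1 v 6 | 0.63 | 0.73 | 0.81 |
| 1 v 6, an earlier visit (mean 2–3 months) can set the date | 0.76–0.77 | – | – |
| 4 v 1 | 0.93 | – | – |
| 6 v 1 | 0.95 | – | – |

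Switch-censoring in both arms, equal 2-month waits, 50% share:
- Week-12 failures: 0.5 × 103 = 51.5.
- A quarter censored: 103 − 12.9 = about 90 events, power about 0.78.
- Half censored: 103 − 25.8 = about 77 events, power about 0.71 (0.70 to 0.72 across runs).
- The HR stays near 0.52, so the loss is in information.
- At a 10% share, power is 0.81 to 0.83.

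**The case against.** **The Protocol does state a date.** A reader might infer that the documents offer no date rule, or two rival dates. Neither is right. Protocol 7.1.1 gives a rule, the SAP states no competing date, and the Table 4.1 columns fit the Protocol rule. What stands is narrower: the subsequent event is not defined, there is no fallback, and the SAP wording makes the failure itself the event.

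**Protocol 11.2 hints at event-first logic.** Its closing clause, on leaving the group with no episode, suggests that an episode already experienced counts. But it is attached to leaving the group, and it does not settle a patient whose dated event is still to come.

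**Precedence comes from switch-censoring sitting beside intention-to-treat.** True: dropping switch-censoring would dissolve it. While Protocol 11.2 stands, the conflict stands, and its effect on event counts should not be credited to dating.

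**Much larger effects can be imagined.** A reader might infer that late failures drop out of the analysis, or that switch-censoring falls on one arm and biases the result in a known direction. SAP 7.1 counts late failures, and no text directs one-arm censoring. In the drug arm, the switch described in 8.3 is ablation, which may be the very procedure that dates the event; the usual convention then counts it.

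**Attendance dating has merit.** The endpoint was chosen because attendances are objective, and Protocol 8.4 requires a letter for adjudication. That is a fair reason to keep the 7.1.1 date, and this review does not hold week 12 to be the only defensible choice.

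**Conclusion.** The concern holds as a conflict over one class of primary event. Following Protocol 7.1.1 and 11.2 literally can leave some week-12 failures undated and censor others. That runs against SAP 7.1, the intention-to-treat statements in both documents, and Protocol 13.2.

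Its size is unknown. Equal waits hardly matter. If half of events are week-12 failures, waits of 1 v 4 or 1 v 6 months would give power of about 0.69 or 0.63, and reversing the waits raises power instead. If an earlier visit can set the date, 1 v 6 gives 0.76 to 0.77. Censoring a quarter or half of the failures in both arms costs about 13 or 26 of the 103 planned events. If week-12 failures are a tenth of events, the effects are small. All of this rests on assumed shares, waits and switch rates, and the direction of any bias cannot be stated. It should be fixed before the analysis because the choice affects primary event counts and the cure is cheap.

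**What to change.** Amend Protocol 7.1.1 and 11.2, and SAP 7.1 and 8.2, with the same text in both documents:

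1. Every week-12 discharge failure is a primary event. It is not displaced by a later treatment switch or by the absence of a later visit.
2. One date rule applies to all arms. Either use the Week 12 review date, or keep the 7.1.1 date, defined as the first subsequent outpatient visit or procedure, with a stated fallback date within follow-up (for example month 12) when that event is missing or late.
3. The other date is reported as a sensitivity analysis.

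**Cost.** A few sentences in two documents and one extra analysis. Week-12 dating needs no new data, since Protocol 6.5 already provides for it: "Patient will be assessed at week 12 for evidence of Primary and secondary endpoints". Its drawback is that the event is placed at an unblinded decision rather than a documented attendance, which is why the other date is kept as a sensitivity analysis. It also creates more tied times, with little effect: with every week-12 failure on one day, power stays at 0.83 and the HR is 0.55 with Breslow ties or 0.53 with Efron ties.
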